2.5.4 Windows for time points

Visit windows based on days relative to the first IMP administration will be used to map the efficacy parameters (Table 6), selected safety variables (Table 7) and PK/PD variables (Table 8) to each scheduled visit. Date of randomization will be used as the reference date for patients not treated. The following rules will be applied:

1. For efficacy parameters, only scheduled measurements will be considered. If a patient has more than one measurement for the same parameter at different dates within the same visit window, the one that is closest to the target date will be used (or the latest in case of tie).
2. Only values from the central laboratory will be considered for laboratory variables.
3. For the same laboratory/vital sign/ECG/PK/PD parameter, if a patient has more than one measurement at different dates within the same visit window, the measurement that is closest to the target date will be used (or the latest in case of tie).
4. When a patient has more than one measurement on the same laboratory/vital sign/ECG/PK/PD parameter on the same date, then the one with the later/largest sample ID will be used.
5. For procedures planned on Visit 2, if it is done on the same date as the first IMP but the performance time is missing, it will be assigned to the Visit 2 time window.

Table 6 – Time window for efficacy endpoints

Visit	Target Day	Pre-BD spirometry	Post-BD spirometry
Visit 1 (Wk-4 to Wk-1)	-28±3	-28±3	-28±3
Visit 2 (Week 0)	1	≤1	≤1
Visit 3 (Week 2)	15	2-21	2-21
Visit 4 (Week 4)	29	22-42	22-42
Visit 6 (Week 8)	57	43-70	43-70
Visit 8 (Week 12)	85	71-98	71-126
Visit 10 (Week 16)	113	99-126	
Visit 12 (Week 20)	141	127-154	
Visit 14 (Week 24)	169	155-182	127-266
Visit 16 (Week 28)	197	183-210	
Visit 18 (Week 32)	225	211-238	
Visit 20 (Week 36)	253	239-266	
Visit 22 (Week 40)	281	267-294	
Visit 24 (Week 44)	309	295-322	
Visit 26 (Week 48)	337	323-343	
Visit 27 (Week 50)	351	344-357	
EOT (Week 52)	365	358-392	267-392
F1 (Week 60)	421	393-462	393-462
EOS (Week 72)	505	≥463	≥463

Table 7 – Time window for safety endpoints

Visit	Target Day	Vital signs	ECG	Hematology, biochemistry, urinalysis	Heptitis and HIV serology tests, quantiferon gold testing, serum pregnancy test	Urine pregnancy test
Visit 1 (Week -4 - 0)	-28±3	< -7	<-7	<-7	≤1	
Visit 2 (Week 0)	1	-7-1	-7-1	-7-1		≤1
Visit 3 (Week 2)	15	2-21				
Visit 4 (Week 4)	29	22-35				2-42
Visit 5 (Week 6)	43	36-49				
Visit 6 (Week 8)	57	50-63		2-84		43-70
Visit 7 (Week 10)	71	64-77				
Visit 8 (Week 12)	85	78-91	2-126			71-98
Visit 9 (Week 14)	99	92-105				
Visit 10 (Week 16)	113	106-119		85-140		99-126
Visit 11 (Week 18)	127	120-133				
Visit 12 (Week 20)	141	134-147				127-154
Visit 13 (Week 22)	155	148-161				
Visit 14 (Week 24)	169	162-175	127-210	141-210		155-182
Visit 15 (Week 26)	183	176-189				
Visit 16 (Week 28)	197	190-203				183-210
Visit 17 (Week 30)	211	204-217				
Visit 18 (Week 32)	225	218-231				211-238
Visit 19 (Week 34)	239	232-245				
Visit 20 (Week 36)	253	246-259	211-308	211-308		239-266
Visit 21 (Week 38)	267	260-273				
Visit 22 (Week 40)	281	274-287				267-294
Visit 23 (Week 42)	295	288-301				
Visit 24 (Week 44)	309	302-315				295-322
Visit 25 (Week 46)	323	316-329				

Visit 26 (Week 48)	337	330-343			323-350
Visit 27 (Week 50)	351	344-357			
EOT (Week 52)	365	358-392	309-434	309-434	351-434
F1 (Week 60)	421	393-462			
EOS (Week 72)	505	≥463	≥435	≥435	≥435

Table 8 – Time window for PK/PD endpoints

Visit	Target Day	Serum SAR440340 concentration	Anti-drug antibody	Blood eosinophil /neutrophil	FeNO	Total IL33, sST2, calcitonin	PARC, eotaxin-3	Total IgE	Fibrinogen
Visit 1 (Week -4 - 0)	-28±3			<-7		<-7	<-7	<-7	<-7
Visit 2 (Week 0)	1	≤1	≤1	-7 - 1	≤1	-7 - 1	-7 - 1	-7 - 1	-7 - 1
Visit 3 (Week 2)	15	2-21							
Visit 4 (Week 4)	29	22-42		2-42	2-42	2-42	2-42	2-42	
Visit 6 (Week 8)	57	43-70		43-70	43-70	43-70			
Visit 8 (Week 12)	85	71-98	2-126	71-126	71-126	71-126	43-126	43-126	
Visit 10 (Week 16)	113	99-140							
Visit 14 (Week 24)	169	141-210	127-266	127-210	127-210	127-266	127-210	127-266	2-266
Visit 20 (Week 36)	253	211-308		211-308	≥211		211-308		
EOT (Week 52)	365	309-392	267-434	309-392		267-392	≥309	≥267	≥267
F1 (Week 60)	421	393-462		393-462		393-462			
EOS (Week 72)	505	≥463	≥435	≥463		≥463			

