β-hCG = Human chorionic gonadotropin-beta; BID = twice daily assessments; CAT = COPD Assessment Test; continuous = subsequent visits during the treatment period; COPD = chronic obstructive pulmonary disease; cont. = continuous; DNA = Deoxyribonucleic acid ; EDTA = Ethylenediaminetetraacetic acid ; EOS = End of Study; EOT = End of treatment; EQ-5D= Euro Quality of Life-5 Dimension questionnaire; EXACT = Exacerbations of COPD tool (EXACT); HIV = human immunodeficiency virus; IgE = Immunoglobulin E; IMP = Investigational Medical Product; IVRS = Interactive Voice Response System; IWRS = Interactive Web Response System; LABA = Long-acting β2 adrenergic agonist; LAMA = Long-acting muscarinic antagonist ;PARC = Pulmonary and activation-regulated chemokine; PK = Pharmacokinetic; RNA = Ribonucleic acid; SABA = Short-acting beta-agonists; SAEs = Serious adverse events; SC = subcutaneous; SGRQ = St. George's Respiratory Questionnaire.

a Randomization/baseline Visit is defined as Day 1. The visit schedule should be adhered to within ±3 days for the screening period and randomized IMP treatment period, and ±5 days for the 2 visits during the post IMP treatment period.

b All assessments at Visit 2 (Day 1) are to be conducted pre-IMP dose with the exception of the assessment of local tolerability of SC injections.

c End-of-treatment visit: See Section 4.1 for patients who discontinue treatment.

d Can be performed with a phone call.

e Chest X-ray to be performed unless a <6 month old chest x-ray/chest CT/chest MRI is available. In case chest-X-ray is not feasible due to local regulations, magnetic resonance imaging (MRI) will be performed.

f The COPD Assessment Test (CAT) is to be registered through the patient's electronic diary.

g IMP (SAR440340 or placebo) to be administered every 2 weeks at the site. Last dose will be given 2 weeks prior to planned EOT visit eg, for patients with 52-week treatment period the last dose will be taken at Week 50, or earlier, as directed by the sponsor. Patients should be monitored by site personnel for at least 30 minutes after administration of all IMP injections. Monitoring period may be extended as per country specific requirements.

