1 OVERVIEW AND INVESTIGATIONAL PLAN

1.1 STUDY DESIGN AND RANDOMIZATION

This is a multinational, randomized, double-blind, placebo controlled, parallel group (2 groups), Proof of Concept (PoC) study assessing the efficacy, safety, and tolerability of SAR440340 (also referred to as REGN3500) in patients with moderate-to-severe COPD on a combination of long-

acting β 2 adrenergic agonist (LABA), long-acting muscarinic antagonist (LAMA), and/or inhaled corticosteroid (ICS) background therapy (as double or triple therapy of any combination). Patients will be treated with SAR440340 or placebo for a minimum of 24 weeks and up to a maximum of 52 weeks, followed by a 20-week post treatment follow-up period.

This study employs a variable treatment duration from 24 to 52 weeks to maximize data for the primary endpoint (annualized rate of exacerbation) in a time-efficient manner. Patients enrolled in the trial will remain in the treatment period for maximally 52 weeks or minimally until 24 weeks after the last patient is randomized, whichever is earlier.

The study duration is outlined below:

- Screening period (10 days to 4 weeks)
- Randomized investigational medicinal product (IMP) treatment period (24 to 52 weeks)
- Post IMP safety follow-up period (20 weeks).

Patients must be on Standard of Care background therapy for at least 3 months prior to Visit 2 (Randomization) and on a stable dose for at least 1 month prior to Visit 1 (Screening), including either:

- Double therapy: LABA + LAMA or ICS + LABA or ICS + LAMA.
- OR
- Triple therapy: ICS + LABA + LAMA.

Patients who satisfy the inclusion and exclusion criteria will be randomized (1:1) to:

- SAR440340 (300 mg) administered as 2 SC injections every 2 weeks (q2w) for 24 to 52 weeks
- Matching placebo for SAR440340 administered as 2 SC injections q2w for 24 to 52 weeks

Upon completing the 24-52 weeks randomized IMP treatment or early permanent treatment discontinuation, patients will continue their established background therapy and enter the 20-week post treatment follow-up period.

Approximately 340 patients will be randomized in this study (170 patients per arm). Randomization will be stratified by blood eosinophil count at Visit 1 (Screening) ($<250 /\text{mm}^3$ vs $\geq 250 /\text{mm}^3$) and country. Alerts will be built into an interactive response technology (IRT) system to balance the number of patients enrolled in the two eosinophil strata:

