1.3 DETERMINATION OF SAMPLE SIZE

To assess the power of the primary efficacy endpoint the annualized rate of moderate-to-severe AECOPD, we assume

- Average of 1.0 to 1.5 AECOPD per year in the placebo group of this study population enriched for severity and high risk of AECOPD.
- The number of AECOPD follows a negative binomial distribution with dispersion parameter 1.5 for all the groups.
- A Wald-test is used to test whether the risk ratio is 1 with 2-sided 5% significance level.
- Patients will be treated with a minimum of 24 weeks and a maximum of 52 weeks depending on their study entry times. The monthly cumulative patient accruals are assumed to be 1, 5, 10, 25, 50, 90, 150, 210, 270, 335 and 340 for an eleven (11)-month accrual period.

- Cumulatively, 9%, 15% and 20% of patients drop out of the study due to discontinuation or other reasons by 12, 24 and 52 weeks after study entry.
- Patients are randomized to the treatment group and the placebo group with a 1:1 ratio.

With these assumptions and 170 patients per group (340 patients in total), the study will yield 81.6% to 88.8% powers with risk reduction equal to 45% in rate of AECOPD and the placebo rate ranging from 1.0 to 1.5 per year. To obtain at least 80% power, the minimum risk reduction is from 44.2% to 40.6%. The minimum detectable risk reduction (i.e. with 50% power) is from 32.7% to 30.0%. See the table below for more details.

Table 1 - Power calculation for various AECOPD event rates in the placebo group

Placebo rate	Power for certain Risk Reduction (RR)			Minimum RR for certain power	
	RR=40%	RR=45%	RR=50%	Power=80%	Power=50%
1.0	69.9%	81.6%	90.3%	44.2%	32.7%
1.2	74.1%	85.2%	92.9%	42.5%	31.4%
1.5	78.5%	88.8%	95.2%	40.6%	30.0%

RR: risk reduction

Based on the accrual and drop-out assumptions, the mean exposure time is 35.5 (\pm 12.8) weeks. Since we use variable follow-up times for patients entering at different times, the power will depend on the actual accrual rates and the drop-out rates. We will closely monitor these rates. If the accrual rates are significantly lower than planned and/or the drop-out rates are higher than expected, the minimum treatment period may be extended to achieve the desired amount of total exposure. The maximum treatment period of 52 weeks will not be changed.

To assess the key secondary efficacy endpoint, the change from baseline to Week 24 in pre-bronchodilator FEV1, we assume that:

[figure not shown]

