2.1.4 Safety endpoints

The safety analysis will be based on the reported adverse events (AEs) and other safety information, such as clinical laboratory data, vital signs, electrocardiogram (ECG), etc.

Observation period

The observation period will be divided into 4 epochs:

- The **screening** epoch is defined as the time from the signed informed consent date up to the first administration of the IMP.
- The **treatment** epoch is defined as the time from the first administration of the IMP to the last administration of the IMP + 14 days.
- The **residual treatment** epoch is defined as the time from the last administration of the IMP + 15 days to the last administration of the IMP + 154 days.
- If applicable, the **post-treatment** epoch is defined as the time from the last administration of the IMP + 155 days to the patient's end of study (defined as last protocol-planned visit or the resolution/stabilization of all serious adverse events and adverse events with pre-specified monitoring).

The treatment-emergent adverse event (TEAE) period will include both **treatment** and **residual treatment** epochs.

The on-study observation period is defined as the time from the first administration of the IMP to the end of the study.

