2.4.5.3 Analyses of laboratory variables

The summary statistics (including number, mean, median, Q1, Q3, standard deviation, minimum and maximum) of all laboratory variables (central laboratory values and changes from baseline) will be calculated for each visit or study assessment (baseline, each post-baseline time point and last on-treatment) by treatment group. For each continuous parameter listed in [Section 2.1.4.3](#), mean changes from baseline with the corresponding standard error will be plotted over time in each treatment group. This section will be organized by biological function as specified in [Section 2.1.4.3](#).

The incidence of PCSAs (list provided in [Appendix A](#)) at any time during the TEAE period will be summarized by biological function and treatment group whatever the baseline level and/or according to the following baseline status categories:

- Normal/missing
- Abnormal according to PCSA criterion or criteria

For parameters for which no PCSA criteria are defined, similar table(s) using the normal range will be provided.

Laboratory measurements obtained at either scheduled or unscheduled visits will be used in analyses of PCSA. In addition, both centralized and local test results will be used. Centralized data will be used preferentially to the local measures in the analysis when several measurements are performed on the same date and at the same time for a given laboratory test.

Listings will be provided with flags indicating the out of range values as well as the PCSA values.

Potential drug-induced liver injury

The liver function tests, namely AST, ALT, alkaline phosphatase and total bilirubin will be used to assess possible drug-induced liver toxicity. The proportion of patients with PCSA values at any post-baseline visit will also be displayed by duration of exposure for each treatment group.

A graph of distribution of peak values of ALT versus peak values of total bilirubin will also be presented on a logarithmic scale. The graph will be divided into 4 quadrants with a vertical line corresponding to 3 x ULN for ALT and a horizontal line corresponding to 2 x ULN for total bilirubin.

Listing of selected laboratory parameters for possible Hy's law cases identified by treatment group (eg, patients with any elevated ALT >3 x ULN, and associated with an increase in bilirubin ≥ 2 x ULN) will be provided.

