4 DATABASE LOCK

A core database lock is planned to occur approximately 4 weeks after the last EOT visit. The final database is planned to be locked 4 weeks after last patient last visit.

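### Fixed-day visit windows place follow-up visits in late treatment-visit rows for patients whose planned treatment is shorter than 52 weeks

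*SAP*

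**What the plan says.** Under SAP 1.1, patients "will remain in the treatment period for maximally 52 weeks or minimally until 24 weeks after the last patient is randomized", whichever comes first, followed by 20 weeks of follow-up. In the protocol's schedule (1.3.1), F1 is 8 weeks and EOS 20 weeks after EOT. The dosing footnote adds: "Last dose will be given 2 weeks prior to planned EOT visit".

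SAP 2.5.4: "Visit windows based on days relative to the first IMP administration will be used to map the efficacy parameters". The same reference day governs the safety (Table 7) and PK/PD (Table 8) windows. EOT, F1 and EOS have single target days of 365, 421 and 505. For efficacy, only scheduled measurements count. When several values fall in one window, the one nearest the target is kept, or the latest if tied. SAP 2.4.5 sends all safety values through these windows, and 2.5.5 covers unscheduled visits only.

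SAP 4: "A core database lock is planned to occur approximately 4 weeks after the last EOT visit". The final lock follows 4 weeks after the last patient's last visit. The section does not assign outputs to locks.

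**The concern.** The target days are right only for a patient with a 52-week plan. For a shorter plan, F1 and EOS fall on earlier study days, inside windows labelled as treatment visits. They are scheduled visits, so the scheduled-only rule lets them through. The limit to planned treatment duration in SAP 2.4.4.1 is written for exacerbations, and the 14-day limit for FEV1 in 2.4.4.2.1 applies only to a sensitivity analysis.

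At stake are the MMRMs up to Week 52 (FEV1 and FVC), which report estimates, intervals and p-values at each time point, and the late by-visit PK, PD and safety rows. These would mix treatment-period values with values taken about 10 or 22 weeks after the last dose. An apparent late fall in drug concentration, for example, could come from labelling alone. SGRQ and EQ-5D are also collected at F1 and EOS and enter an MMRM to Week 52, but have no window in Table 6.

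**Working it through.** **Inputs.** Cumulative monthly accrual is 1, 5, 10, 25, 50, 90, 150, 210, 270, 335, 340, and cumulative dropout is 9%, 15% and 20% by Weeks 12, 24 and 52 (SAP 1.3). Windows come from Tables 6 to 8. Sampling visits come from SAP 2.1.4 to 2.1.7 and Protocol 1.3.1, where a footnote adds a complete hematology panel at F1.

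**Formulas.** For entry at month m (uniform within a month), planned duration is D = min(52, 24 + (11 − m) × 52/12) weeks. EOT day is E = 7D + 1, F1 = E + 56, EOS = E + 140.

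**The plan's own figure.** With linear dropout between the stated points, mean exposure is 35.5 (SD 12.8) weeks, as SAP 1.3 states.

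**Full 52 weeks.** This needs (11 − m) × 4.333 ≥ 28, so m ≤ 4.54. Cumulative accrual there is 25 + 0.54 × 25 = 38.5, about 38 of 340.

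**One patient, EOT at Week 30.** E = 211, F1 = 267, EOS = 351. Pre-bronchodilator FEV1 at F1 becomes Week 40 (267-294) and at EOS becomes Week 50 (344-357). For PK, the Week 36 window is 211-308 with target 253. F1 is 14 days away and the true EOT 42 days away, so F1 is used and the EOT value is not. EOS falls in 309-392 and is labelled EOT (Week 52).

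**PK, EOT (Week 52) row, window 309-392.** EOS enters when E is 169-252 and F1 when E is 253-336. Together these cover every plan from 24 to just under 48 weeks. Where EOT and F1 both fall inside, F1 is nearer to Day 365 because E + 28 < 365.
- EOT rounded down to a two-weekly visit: D < 48 means m > 5.46, where accrual is 50 + 0.46 × 40 ≈ 68. Then 340 − 68 = 272, or 80%.
- Rounded up: D ≤ 46 means m ≥ 5.92, where accrual is about 87. Then 253, or 74%.

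**Chemistry, EOT (Week 52) row, window 309-434, no F1 sample, exact timing.** EOS enters for D up to about 41.9 (m ≥ 6.86, accrual 142): 340 − 142 = 198 patients. EOT itself enters for D of at least about 43.9 (m ≤ 6.40): 114 patients. The share is 198/312 = 63%.

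**Follow-up share, planned accrual, no dropout, on-target visits.** Ranges cover EOT exact or rounded down, to nearest or up.

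| Row | Share | Values in row |
|---|---|---|
| Pre-BD FEV1 Week 32 | 0-2 patients | |
| Pre-BD FEV1 Week 36 | 2-10% | 279-285 |
| Pre-BD FEV1 Week 40 | 20-23% | 254-279 |
| Pre-BD FEV1 Week 48 | 35-49% | 141-174 |
| Pre-BD FEV1 Week 52 | 69-74% | 139-175 |
| EOT (Week 52): post-BD FEV1, PK, eosinophils/neutrophils (Table 8), IL33/sST2/calcitonin | 74-80% | 340 (PK 170) |
| EOT (Week 52): hematology | 80-85% | 340 |
| EOT (Week 52): chemistry, urinalysis, ECG | 55-64% | about 312 |
| Week 36: PK, eosinophils/neutrophils, hematology | 18-26% | 340 (PK 170) |
| Week 36: chemistry, ECG | 0% | |

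Pre-BD Week 50 is 74-83% of 70-73 values if spirometry is not routine at Week 50. If it is routine, the share is about half (49% with exact timing). EOS reaches the EOT row for planned EOT up to about Week 36 (spirometry, PK) or Week 41 (ECG, laboratory).

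**Displaced EOT values in the EOT (Week 52) row.** 128-137 of 340 for post-BD FEV1 and IL33/sST2/calcitonin; 45-54 for PK and eosinophils/neutrophils.

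**Sensitivity.** The protocol allows visits to move by ±"3 days for the screening period and randomized IMP treatment period, and ±5 days for the 2 visits during the post IMP treatment period". With that jitter, pre-BD Week 52 is 73-76%, PK 76-82% and chemistry 59-67%. Planned dropout moves the shares by less than 1 point. SAP 1.3 also says "the minimum treatment period may be extended to achieve the desired amount of total exposure". A 28-week minimum gives PK 59-67%, pre-BD Week 52 49-62% and chemistry 37-46%. A 32-week minimum gives 42-51%, 29-37% and 19-28%. With uniform accrual over 11 months, or accrual 1.5 times longer, the EOT rows are about 33-51% with exact timing.

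**Locks.** Shortened-plan patients share one cut-off date. Their F1 comes about 8 weeks after it and the core lock about 4 weeks after it, so none of the 253-272 patients whose F1 is misplaced in or before the EOT (Week 52) window has an F1 value at the core lock. The pre-BD Week 52 row then grows from 38-50 values at the core lock to 139-175 at the final lock.

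**The case against.** The best defence is that little of consequence depends on these rows. The study is Phase 2a with nominal p-values, the MMRMs to Week 52 are supplementary, the by-visit tables are descriptive, and core-lock outputs are clean for planned completers. All of that stands, and it limits the severity.

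It is also fair that the large shares reflect the planned back-loaded accrual. A reader might infer that follow-up values will form most of every late row whatever happens. The documents do not support that: slower or flatter accrual, or a longer minimum treatment period, takes several EOT rows below one half. Mixing remains in each of these scenarios.

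Nor does the point cover every biomarker. PARC, eotaxin-3, total IgE and fibrinogen have no F1 or EOS samples, so their rows are clean. The Week 50 share rests on a schedule row that is hard to read in the available text, and should carry little weight.

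A programmer might well assign F1 and EOS by nominal visit in practice, but the SAP as written says otherwise.

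**Conclusion.** The windowing rule is wrong as written for a variable-duration trial, and the severity is modest. At the final lock it mislabels follow-up values as treatment visits, from Weeks 36-40 onward in material numbers for pre-bronchodilator FEV1 and at Week 36 for PK, eosinophils/neutrophils and hematology. Under the planned accrual, follow-up values form 55-85% of the affected EOT (Week 52) rows listed above. Those percentages depend on accrual; the mechanism does not. The size of any resulting bias cannot be estimated from the documents.

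A reader might infer that the efficacy conclusions or safety counts are compromised. They are not, in planned completers. The primary rate and time to first AECOPD do not use these windows, and the key secondary windows end at Day 182, before the earliest F1 (Day 225). The post-bronchodilator Week 24 window (127-266) could take an F1 value only for EOT before about Week 30, and only if the nearer Week 24 and EOT values were both missing. PCSA incidence and the safety endpoint value do not depend on the visit rows. On-schedule F1 and EOS also lie inside the treatment-emergent period, whose residual epoch runs from "the last administration of the IMP + 15 days to the last administration of the IMP + 154 days". For safety this is row labelling only.

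**What to change.** Before the final lock, amend SAP 2.5.4 as follows.

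- Assign every visit recorded as F1 or EOS by nominal visit to its own row. Exclude it from the MMRMs up to Week 52 and from treatment-visit rows.
- Keep EOT and scheduled treatment-period visits, including those after an early stop of IMP, in study-day windows up to the patient's planned EOT plus the visit allowance.
- Assign unscheduled safety values after the planned EOT to follow-up rows by days from the patient's own EOT, so that 2.4.5 and 2.5.5 still hold.
- Apply the same rule to SGRQ and EQ-5D.
- In section 4, state which outputs use the core and which the final lock.

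SAP 1.1 sends early discontinuers into follow-up, whereas Protocol 4.1 asks them to complete the remaining treatment visits. These passages must be reconciled before the rule is applied to such patients.

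The cost is SAP wording and one derivation, with no new data. Late rows shrink: pre-BD Week 52 to about 38-50 values rather than 139-175, and EOT (Week 52) eosinophils to 113-141 rather than 340 (PK half of each). An EOT row pooled over treatment durations could be added as a separate summary.

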Pharmacokinetics																																											
Serum samples for SAR440340 concentration ^o		X	X	X		X		X		X				X																							X	X		X			
Anti-SAR440340 antibody ^p		X						X						X																								X			X		
Biomarkers																																											
Blood eosinophils and neutrophils	X	X		X ^q		X		X ^q						X																							X	X ^q		X			
Total IL33 and sST2 ^o	X	X		X		X		X						X																								X	X		X		
Calcitonin	X	X		X		X		X						X																								X	X		X		
PARC	X	X		X				X						X																								X					
Eotaxin-3	X	X		X				X						X																								X					
Total IgE	X	X		X				X						X																								X					
Fibrinogen	X	X												X																							X						
FeNO pre-bronchodilator (optional) ^f		X		X		X		X						X																													
FeNO post-bronchodilator (optional) ^f		X		X		X		X						X																													
Induced sputum (optional) ^s		X												X																									X				
Blood samples for RNA sample (optional)	X	X		X										X																									X				
Blood sample archival for exploratory research (optional) ^t	X	X		X				X						X																										X			

	S	R/ B																																		
VISIT	1	2 ^{a, b}	3	4	5	6	7	8	9	10	11	12	13	14	15	16	17	18	19	20	21	22	23	24	25	26	27	EOT ^c	F1	F2 ^d	EOS					
WEEK	W-4 to W-1	0	2	4	6	8	10	12	14	16	18	20	22	24	26	28	30	32	34	36	38	40	42	44	46	48	50	52	60	66	72					
DNA Pharmacogenomics analysis (optional)		X																																		
Efficacy																																				
COPD exacerbation reporting by the Investigator		X	X	X	X	X	X	X	X	X	X	X	X	X	X	X	X	X	X	X	X	X	X	X	X	X	X	X	X	X	X	X	X	X		
Spirometry (pre-BD) ^{u, v}	X	X	X	X		X		X		X		X		X		X		X		X		X		X		X		X		X		X		X		
Spirometry (post-BD) ^{u, v}	X	X	X	X		X		X					X							X								X				X		X		
EXACT ^w	Every day (diary) from screening to week 52																																			
SGRQ ^w		X		X		X		X						X						X								X		X		X		X		
EQ-5D-5L ^w		X												X														X		X		X		X		
Actigraphy Optional assessments (US/Canada only)	Co n- tin uous							Con- tinuos						Con- tinuos																						
At-home spirometry (FEV1) Optional assessments (US/Canada only)	BI D							BID						BID																						

S= Screening; R/B= Randomization/Baseline; F=Follow-up

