2.1.3.3.1 Patient-reported outcomes

COPD Assessment Test (CAT)

The CAT is a short, validated, patient-completed questionnaire to assess the impact of COPD on health status (see [Appendix C](#)). It comprises 8 questions that cover a broad range of effects of COPD on patients' health. Each question is scored in a range between 0 (I am very happy) and 5 (I am very sad), with the higher end indicating a higher impact of COPD on the patient's wellbeing. The CAT total score, the sum of the 8 individual question scores, ranges from 0 (best) to 40 (worst). This score is collected only at screening and baseline to assess patient eligibility.

St. George's respiratory questionnaire (SGRQ)

St. George's Respiratory Questionnaire (SGRQ) is a 50-item PRO instrument developed to measure the health status of patients with airway obstruction diseases (see [Appendix E](#)). The questionnaire is divided into two parts: part one consists of eight items pertaining to the severity of respiratory symptoms in the preceding 4 weeks; part two consists of 42 items related to the daily activity and psychosocial impacts of the individual's respiratory condition.

The SGRQ yields a total score and three domain scores (symptoms, activity, and impacts). The total score indicates the impact of disease on overall health status. This total score is expressed as a percentage of overall impairment; 100 represents the worst possible health status and 0 indicates the best possible health status (minimal clinically important difference: -4 units). Likewise, the domain scores range from 0-100, with greater scores indicative of greater impairment. See [Appendix F](#) for the scoring algorithm.

This questionnaire is assessed at baseline and at weeks 4, 8, 12, 24, 36, 52, 60 and 72.

Exacerbations of chronic obstructive pulmonary disease tool (EXACT)

The EXACT is a 14-item daily diary designed to provide a direct measure of patient-reported symptoms of COPD exacerbation (see [Appendix B](#)) and covers the following domains:

- Breathlessness (5 items),
- Cough and sputum (2 items),
- Chest symptoms (3 items),
- Difficulty bringing up sputum (1 item),
- Tired or weak (1 item),
- Sleep disturbance (1 item), and
- Scared or worried (1 item).

It is completed each evening before bedtime.

The EXACT total score is an interval-level scale ranging from 0 to 100, where higher scores indicate a more severe condition.

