2.1.7 Pharmacodynamic (PD)/genomics endpoints

PD endpoints include:

- **Whole blood biomarkers:** blood eosinophil and neutrophil count measured at Visits 1, 2, 4, 6, 8, 14, 20, EOT, F1 and EOS.
- **Serum biomarkers:** total interleukin-33 (IL33), soluble IL33 receptor (sST2) and calcitonin assayed at Visits 1, 2, 4, 6, 8, 14, EOT, F1 and EOS; Total IgE measured at Visits 1, 2, 4, 8, 14 and EOT; pulmonary and activation-regulated chemokine (PARC) measured at Visits 1, 2, 4, 8, 14, 20 and EOT.
- **Plasma biomarkers:** Eotaxin-3 measured at Visits 1, 2, 4, 8, 14, 20 and EOT.
- **Fibrinogen** measured at Visits 1, 2, 14 and EOT.
- Optional PD endpoints (for patients who provide a separate consent for each individual test) include:
 - Pre- and post-bronchodilator FeNO (Fractional exhaled nitric oxide) at Visits 2, 4, 6, 8, 14, 20.
 - Induced sputum for RNA expression at Visits 2, 14 and EOT.
 - RNA samples collected at Visits 1, 2, 4, 14 and EOT.
 - Archived blood samples collected at Visits 1, 2, 4, 8, 14, 20 and EOT.

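### SAP Table 6 gives post-bronchodilator FEV1 no Week 36 window, so the scheduled Visit 20 test is either discarded or analysed as Week 24

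*SAP*

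**What the plan says.** SAP Section 2.5.4 maps efficacy measurements to visits by study day. In Table 6 the last two entries of each full row are the pre- and post-bronchodilator windows. The Week 24 row reads "Visit 14 (Week 24) 169 155-182 127-266" and the end-of-treatment row "EOT (Week 52) 365 358-392 267-392". The Visit 20 (Week 36) row has target day 253 and a pre-bronchodilator window of 239-266, with nothing in the post-bronchodilator column. Rule 1 of that section admits only scheduled measurements and, when several fall in one window, keeps the one nearest the target day.

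The post-bronchodilator row of the Schedule of Activities (Protocol Section 1.3.1) carries a mark at Visit 20. Footnote a sets the tolerance: "The visit schedule should be adhered to within ±3 days" in the treatment period.

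Protocol Section 9.4.1, Table 14, plans to analyse change in FEV1 after Week 24 both before and after bronchodilator. SAP Section 2.4.4.2.2 says the post-bronchodilator analysis follows that of the key secondary endpoint. The latter (Section 2.4.4.2.1) includes a repeated-measures model to Week 52 with estimates at every measured time point. SAP Section 1.5, which lists departures from the protocol's statistical section, mentions no removal of a post-bronchodilator time point.

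**The concern.** A scheduled measurement has no analysis visit of its own and lies inside the window of another. Two things follow. First, no Week 36 post-bronchodilator estimate can be produced under the written rules, although the protocol plans analysis past Week 24. Second, a patient with no post-bronchodilator value nearer to day 169 would have the Week 36 value entered as Week 24. Change to Week 24 in post-bronchodilator FEV1 is a named secondary endpoint, so a value about 12 weeks late could enter it without being flagged.

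**Working it through.** **1. Reproduce the printed windows.** Target days are 7 × week + 1: Week 12 = 85, Week 24 = 169, Week 36 = 253, Week 52 = 365, Week 60 = 421. Splitting at midpoints and leaving Week 36 out:

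- Week 12 / Week 24: (85 + 169)/2 = 127
- Week 24 / Week 52: (169 + 365)/2 = 267
- Week 52 / Week 60: (365 + 421)/2 = 393

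This gives Week 24 = 127-266 and end of treatment = 267-392, exactly as printed. The two windows adjoin, so the empty Visit 20 cell belongs to the table as built and was not lost in reading the PDF.

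**2. Is a Week 36 test scheduled?** The Schedule of Activities row is partly shifted in the available text; its Week 24 mark, for example, stands one column early. Two observations do not depend on that mark:

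- The row has 11 marks and the post-bronchodilator column of Table 6 has 10 windows. Both have two entries after end of treatment. Between Visit 8 and end of treatment the schedule has two marks and Table 6 has one window.
- The second of those marks is in column 20, as is a mark in the SGRQ row. For the SGRQ the SAP states "This questionnaire is assessed at baseline and at weeks 4, 8, 12, 24, 36, 52, 60 and 72", so column 20 is Week 36 in that row.

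**3. Where the Visit 20 test goes.** Day 253 ± 3 = 250-256, which lies within 127-266. Distance from the Week 24 target: 250 − 169 = 81 to 256 − 169 = 87 days. A Visit 14 test (169 ± 3) is always closer, so the Visit 20 value is discarded. Without a closer scheduled value, the Visit 20 value becomes the Week 24 value.

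**4. What the SAP does for comparable schedules.**

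| Variable | Measured at Visit 20? | Week 24 | Week 36 | End of treatment |
|---|---|---|---|---|
| Total IL33, sST2, calcitonin (Table 8) | No: "calcitonin assayed at Visits 1, 2, 4, 6, 8, 14, EOT, F1 and EOS" | 127-266 | none | 267-392 |
| Blood eosinophils/neutrophils (Table 8) | Yes: "blood eosinophil and neutrophil count measured at Visits 1, 2, 4, 6, 8, 14, 20, EOT, F1 and EOS" | 127-210 | 211-308 | 309-392 |
| Post-bronchodilator spirometry (Table 6) | Yes, per the protocol schedule | 127-266 | none | 267-392 |

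The Week 24 row of Table 8 shows both patterns side by side: "Visit 14 (Week 24) 169 141-210 127-266 127-210 127-210 127-266". Post-bronchodilator spirometry has the windows of variables not measured at Week 36.

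**5. Windows with Week 36 included.** (169 + 253)/2 = 211 and (253 + 365)/2 = 309. Hence Week 24 = 127-210, Week 36 = 211-308, end of treatment = 309-392, matching the eosinophil windows.

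**6. How many tests are involved.** Inputs are from SAP Section 1.3: cumulative monthly accrual 1, 5, 10, 25, 50, 90, 150, 210, 270, 335, 340, and drop-out of 9%, 15% and 20% by Weeks 12, 24 and 52. Assumptions: uniform entry within each month, the last patient entering at the end of month 11, linear drop-out between the stated points, and 4.348 weeks per month.

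- Planned duration = min(52, 24 + weeks until the last entry). This reproduces the stated mean exposure (35.5 weeks) and SD (12.8 weeks).
- At least 36 weeks requires entry by month 11 − 12/4.348 = 8.24: 210 + 0.24 × 60 ≈ 224 patients, and 224/340 = 66%.
- Retained at Week 36: 1 − [0.15 + 0.05 × (36 − 24)/(52 − 24)] = 0.829. Expected tests: 224 × 0.829 ≈ 186.
- If the last patient enters slightly before the end of month 11, the figures are 218 planned and 181 retained.

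**The case against.** Five points can be made on the other side.

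- **The schedule reading.** The Week 36 mark comes from one row of a table broken in extraction, and no SAP section lists a Week 36 post-bronchodilator test. The same table, as extracted, shows no Visit 20 mark for eosinophils although SAP Section 2.1.7 lists that visit, so column position alone is weak evidence. This is a fair caution. The count of marks against windows does not depend on columns, and Week 36 is the natural reading of the extra mark.
- **The SAP's intent.** Section 2.4.4.2.2 qualifies its cross-reference by noting that only Week 24 is available, not Weeks 16 and 20, and the sentence on all time points stands in the pre-bronchodilator section. Read narrowly, the SAP may intend no Week 36 estimate. The qualification does explain why there is no Week 16-24 average. It does not cancel the protocol's plan for post-bronchodilator FEV1 after Week 24, and SAP Section 1.5 records no such change.
- **Make-up tests.** Protocol footnote v sends a missed test to the next visit. A Week 24 make-up at day 183 would be closer to day 169 than a Visit 20 test and would make relabelling rare. Whether Rule 1 counts it as scheduled is not stated, so this remains an expectation.
- **Variable end of treatment.** Because treatment lasts 24 to 52 weeks, about 86 of 340 patients (before drop-out) have a planned end of treatment in Weeks 30-36 under the same accrual model. Under the corrected cells most of those tests would be labelled Week 36. They already fall in the Week 24 window, and the correction moves them to a nearer target day, as the SAP does for eosinophils. It is worth a check but is no reason to keep the present windows.
- **Weight.** This is a Phase 2a study with nominal p-values, and what is mainly lost is one later time point. That is correct and limits the importance of the point.

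**Conclusion.** The point holds. As written, Table 6 leaves no place for the Visit 20 post-bronchodilator test and puts it in the Week 24 window. About 186 such tests (181-186 under the assumptions shown) would have no time point. For most patients the effect is loss of the Week 36 result. For those with no nearer value, a measurement 81-87 days late would serve as Week 24 in a secondary endpoint; their number cannot be derived from the documents and should be small.

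The conclusion rests on the Visit 20 mark in the protocol schedule, on the printed windows and on Rule 1. The accrual and drop-out assumptions affect only the count. The primary endpoint, the key secondary endpoint (pre-bronchodilator FEV1 has its own Week 36 window) and the power figures are unaffected. This is a minor correction that should be made before analysis.

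**What to change.** In the post-bronchodilator column of SAP Table 6, set:

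- Visit 14 (Week 24): 127-210
- Visit 20 (Week 36): 211-308
- End of treatment (Week 52): 309-392

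With these cells, a Week 24 make-up at Visit 15 (day 183) stays in Week 24. A Week 36 make-up at Visit 21 (day 267), which now falls in the end-of-treatment window, goes to Week 36. While editing, it would help to state whether make-up tests count as scheduled under Rule 1, and to confirm that end-of-treatment tests before Week 52 are to be mapped by study day.

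The cost is SAP wording only: three table cells, with no change to data collection, sample size or the analysis model.
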